## 1. Objectives

- 1.1. We propose a non-inferiority randomized controlled trial (RCT) with a primary outcome of lactation continuation through 8 weeks postpartum comparing women receiving immediate (first 24 hours postpartum) versus standard (4-6 weeks postpartum) etonogestrel (ENG) implant insertion. Secondary outcomes include: number of days of postpartum bleeding, time to resumption of sexual activity, postpartum sexual function (measured by Female Sexual Function Index (FSFI) score), and postpartum mood as measured by Edinburgh Postnatal Depression Scale (EPDS) score. We will also measure breastfeeding exclusivity, factors effecting discontinuation of breastfeeding, timing of breast feeding discontinuation, satisfaction with postpartum contraceptive counseling, satisfaction with the contraceptive implant and satisfaction with bleeding pattern in the immediate and standard groups.
- 1.2. The contribution of the proposed research is to determine if immediate ENG implant insertion (within 24 hours) is non-inferior to standard insertion (4-6 weeks) postpartum. We hypothesize that inserting the ENG implant in the first 24 hours postpartum is not inferior to standard insertion at 4-6 week postpartum for breastfeeding continuation through 8 weeks postpartum.
  - 1.2.1. Primary Objective 1: To compare continuation of lactation through eight weeks postpartum between women in the immediate versus standard group. Our hypothesis is that breastfeeding continuation at eight weeks postpartum is not inferior in women in the immediate insertion group of the ENG implant than in those with standard insertion. Our study is powered for this outcome.
- 1.3. Secondary Objectives: To compare number of days of postpartum bleeding, postpartum sexual function as measured by FSFI score, and postpartum mood as measured by EPDS score, time to resumption of sexual activity, exclusive breastfeeding method, factors associated with discontinuing breastfeeding, timing of breastfeeding discontinuation, patient satisfaction with postpartum contraception counseling and the implant and patient satisfaction with bleeding pattern between the immediate and standard insertion groups.

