  - 1.3.1. Secondary Objective 1: To compare the total number of days of postpartum bleeding in the immediate versus standard group at 2, 4, and 8 weeks postpartum . Our hypothesis is that number of days of bleeding in the immediate insertion group is not significantly different than the number of days of bleeding in the standard insertion group.
  - 1.3.2. Secondary Objective 2: To compare postpartum sexual function as measured by Female Sexual Function Index (FSFI) score at 4, 8, and 12 weeks postpartum. Our hypothesis is that FSFI scores for the immediate insertion group are not significantly different than FSFI scores for the standard insertion group.

PROTOCOL TITLE: Effect of immediate versus standard postpartum insertion of the contraceptive implant on breastfeeding outcomes

- 1.3.3. Secondary Objective 3: To compare postpartum mood as measured by EPDS score at 2, 4, and 8 weeks postpartum. Our hypothesis is that EPDS scores for the immediate insertion group are not significantly different than EPDS scores for the standard insertion group.
- 1.3.4. Secondary Objectives 4: To compare exclusive breastfeeding through 6 months postpartum between the immediate versus the standard group.
- 1.3.5. Secondary Objective 5: To compare postpartum factors associated with discontinuing breastfeeding between the immediate versus the standard group.
- 1.3.6. Secondary Objective 6: To compare timing of breastfeeding discontinuation through 6 months postpartum between the immediate versus the standard group.
- 1.3.7. Secondary Objective 7: To compare participant satisfaction with postpartum contraception counseling in women enrolled in the study and in those women who opted not to enroll in the study.
- 1.3.8. Secondary Objective 8: To compare participant satisfaction with timing of ENG implant insertion between the immediate versus the standard group.

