**Regarding secondary objectives:**

1. Bleeding patterns: Irregular bleeding is the most common side effect noted by users of the ENG contraceptive implant. Limited evidence shows that this holds true in the postpartum period (17). In a retrospective cohort study of women who underwent immediate versus standard postpartum insertion of the implant, approximately one in five women requested discontinuation of use due to irregular bleeding, and this rate was not significantly different between the two groups (17). Evidence on the effect of immediate postpartum insertion of the ENG contraceptive implant on lochia is limited and mixed. An RCT of immediate versus standard postpartum insertion of the six-rod levonorgestrel implant showed significantly more total days of bleeding for the immediate insertion group (18), while a more recent Australian prospective cohort study demonstrated no lengthening of the duration of lochia (postpartum bleeding) with immediate insertion (19). We will measure postpartum bleeding patterns using periodic review of a patient bleeding diary that quantifies bleeding on a daily basis as “none”, “spotting”, “bleeding” or “heavy bleeding”. As patient dissatisfaction with irregular bleeding likely mediates discontinuation for this reason, we will also measure patient satisfaction with their bleeding pattern postpartum.

PROTOCOL TITLE: Effect of immediate versus standard postpartum insertion of the contraceptive implant on breastfeeding outcomes

2. Postpartum mood changes: It is possible that postpartum use of an ENG implant may affect postpartum mood. In a retrospective study of adverse event reporting for ENG implant use, it was noted that postpartum depression was a commonly reported adverse event, and therefore may be associated with implant use in the postpartum period (20). In addition, in a secondary analysis study, use of the ENG implant in the postpartum period was associated with a higher risk of later antidepressant use compared to women with no hormonal contraceptive use (21). Women's perception of contraceptives' effect on their mood is a significant factor in contraception discontinuation (22). We hypothesize that timing of implant insertion will not increase postpartum depression related mood changes as measured by the EPDS. We will also assess patient perception of impact of ENG implant insertion on mood.

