5. Factors associated with breastfeeding discontinuation: As mentioned previously, EBF is recommended for 6 months postpartum by the AAP and WHO. It is important to identify and acknowledge these factors to work and plan for counseling and initiatives to improve the length of lactation period. These factors can vary depending of society, culture and even mother's perception. Li et al reported the most common reasons for breastfeeding discontinuation during the first year postpartum were mothers' perception that their infant was not satisfied by breast milk alone and concerns about lactation and nutrition issue. In addition, mothers reported nipple biting and perceived infant loss of interest in breastfeeding (27). Odom et al, found in their study that factors such as difficulties with lactation, infant nutrition and weight, effort to pumping milk, among many others, play an important role in the decision making for lactation cessation (28). With this study, we aim to assess the reason for discontinuation in the mothers who use the implant as a contraceptive method.
6. Satisfaction with postpartum contraception counseling: The American College of Obstetricians and Gynecologists (ACOG) stated in Committee Opinion number 736: Optimizing Postpartum Care that as part of comprehensive postpartum care acknowledging women's reproductive life plan is of vital importance for decision making regarding contraception (1). We aim to explore by a survey how women perceived the counseling: if she understood the counseling and received enough information and time to make a decision about contraceptive choice. This might help to understand women's perception of counseling about postpartum contraception and may be helpful in improving current counseling.
7. Satisfaction with timing of contraceptive implant insertion: Early initiation of a contraceptive method has been recommended as an alternative by ACOG (1). This is because it has been proven that many women miss or do not have a postpartum follow up visit and it is more convenient for women to initiate a method early. When a contraceptive method is started in the postpartum period, it contributes to birth spacing, and maternal and infant wellbeing. We look to understand the satisfaction with having an implant inserted early vs having it inserted in the standard time.

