A research staff will keep a record of contact information for all participants. The staff will schedule visits for standard insertions at 4 weeks postpartum, will contact care provider to let them know the patient is participating in the study and the date of the appointment for the implant insertion. We will schedule standard insertion at 4 weeks postpartum in order to have a 2 week period to reschedule the participant if necessary. UNM appointments can be made at the Center for Reproductive Health Clinic (CRH) for increased convenience and to improve follow up if a participant cannot return to her antepartum clinic.

Research staff will contact participants randomized to the standard insertion group one week before the appointment to remind her of her appointment and will contact the care provider by a message in the EMR to let them know they date of the appointment for the implant insertion. Research staff will coordinate any necessary appointment rescheduling. Research staff will track this information for the purpose of the study CONSORT flow diagram.

Utah's research coordinators will have access to UNM's REDCap and will randomize and enter baseline data. They will also enter the study participants contact information (phone number or email) which is how they will receive the follow up study questionnaires.

UNM will call UNM participants and Utah will call Utah's participants for the follow up for the contact periods at 2, 4, 8, 12, and 24 weeks postpartum will be made by each site's research team to their respective study participants by phone calls, text messages or email. The text message and the emails will include a link to REDCap to access the follow up questionnaire to be completed by the participant. When/if the patient is contacted through phone call the UNM and Utah research staff will only contact their respective participants for completion of the questionnaires in REDCap.

**PROTOCOL TITLE:** Effect of immediate versus standard postpartum insertion of the contraceptive implant on breastfeeding outcomes

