The questionnaires will contain data about breastfeeding, postpartum depression, and sexual function. A paper diary will be provided to aid the participant in daily recording of data. We will also include a retrospective data collection instrument to account for those we miss at the primary data collection points for breastfeeding information. If the primary questions have been answered either prospectively or retrospectively, then they get the normal prospective survey. If participants do not meet this criteria or if they miss a previous survey, then they will receive a retrospective survey. The diary will be collected at 2, 4, and 8 weeks. If possible, 2-3 good phone numbers will be obtained as well as addresses for each participant. Participants will have a phone number to contact study personnel at their specified site during standard work hours: Monday-Friday 8am- 4:30 pm with any concerns or adverse events. If they call after-hours, a voicemail system will be available, and the participant will be contacted the next working day.

*Data collection instruments*

Data collection instrument	Manner of collection	Timing	Included data
Enrollment form	Medical chart review  In-person, telephone and/or online via UNM's REDCap	After delivery  At enrollment	Participant & neonate medical history, delivery details  contraceptive history, contraceptive bridge-methods, lactation history, lactation and work expectations
Contraceptive Counseling Survey	In-person, telephone and/or online via UNM's REDCap	At enrollment and 4 weeks postpartum	Satisfaction with contraceptive counseling
Breastfeeding Survey	In-person, telephone and/or online via UNM's REDCap	2, 4, 8, 12, 24 weeks postpartum	Breastfeeding continuation, exclusivity, reasons for discontinuation if applicable, infant weight, resumption of intercourse, and satisfaction with contraception
EPDS	In-person, telephone and/or online via UNM's REDCap	2, 4, 8 weeks postpartum	Postpartum depression scale
FSFI	In-person, telephone and/or online via UNM's REDCap	4, 8, 12 weeks postpartum	Sexual function scale

PROTOCOL TITLE: Effect of immediate versus standard postpartum insertion of the contraceptive implant on breastfeeding outcomes

Bleeding diary	Paper or UNM's REDCap	Reviewed at 2, 4, 8 weeks. Collected at 2, 4, and 8 weeks	Bleeding patterns Side effects

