## **15. Withdrawal of Subjects**

- 15.1 The research team will provide thorough screening to see if the patient will meet inclusion and exclusion criteria. If any circumstances arise such participant experiencing exclusion criteria during study participation or fail to follow study procedures such as having the implant placed or removed before the study ends, the participant will be notified and withdrawn from the study without their consent.
- 15.2 Participants may have their implant removed at their request at any time. However, removal of the implant automatically terminates participation in the study and no data will be collected further. The data that was already collected from those participants that withdraws or was withdrawn from the study will be used for data analysis.
- 15.3 NA
- 15.4 Participants may withdraw from study involvement at any point in time and this will not affect their ability to obtain standard clinical care that day. All data points will be collected on the date of the procedure and therefore we anticipate loss to follow up and withdrawal rates will be low. Participants will be given the information on how to withdraw in the study consent.
- 15.5 The authorization for the use and disclosure of the participant health information for this study shall not expire unless the participant cancels this authorization. The health information will be used or disclosed as long as it is needed for this study. However, the participant may withdraw her authorization at any time providing a notification to the UNM investigators in writing to notifying the study team about the withdrawal. To do this, a letter should be sent to:

[name]  
Department of Obstetrics and Gynecology  
[name]  
[name]

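### Satisfaction with the implant and its timing is compared between randomised arms, but the withdrawal rules stop follow-up at removal and, on their natural reading, at non-placement, so later comparisons are open to selection after randomisation

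*Combined protocol and SAP*

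**What the plan says.** Two satisfaction outcomes depend on the implant. Section 1.1 lists "satisfaction with the contraceptive implant and satisfaction with bleeding pattern in the immediate and standard groups", and Section 7.1 repeats satisfaction with the implant as a secondary endpoint. Section 1.3.8 sets the objective "To compare participant satisfaction with timing of ENG implant insertion between the immediate versus the standard group", and Section 13.1 includes timing satisfaction among the outcomes tested with simple two-group methods. Section 2.3, item 7, gives the purpose: "We look to understand the satisfaction with having an implant inserted early vs having it inserted in the standard time".

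The Section 7 schedule has a row for satisfaction with counselling, but none for the implant or its timing. The only related item in the Section 12 instruments table belongs to the Breastfeeding Survey and its retrospective counterpart at 2, 4, 8, 12 and 24 weeks: "resumption of intercourse, and satisfaction with contraception". It is not limited to women who hold an implant.

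On insertion, Section 12 says "We will schedule standard insertion at 4 weeks postpartum in order to have a 2 week period to reschedule the participant if necessary". On withdrawal, Section 15.1 covers women who "fail to follow study procedures such as having the implant placed or removed before the study ends, the participant will be notified and withdrawn". Section 15.2 ends participation and further data collection at removal, and keeps what was gathered before. Section 13.1 plans a per-protocol primary analysis and an intention-to-treat secondary analysis, and defines neither set.

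**The concern.** Randomisation protects a comparison only while the women randomised are still measured. Here, two events after randomisation end measurement, and both plausibly relate to satisfaction. A woman who never gets the implant has a view on the timing she was assigned. A woman who has it removed has a view on the implant. Under Sections 15.1 and 15.2, neither view need be recorded.

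The two events may not fall equally. Section 2.3, item 7, justifies the timing objective by saying that "it has been proven that many women miss or do not have a postpartum follow up visit". Those visits are where the standard arm is inserted, so non-placement should fall mainly there. Women who miss the later visit are central to the case for early insertion, and they are the ones the comparison of timing may leave out. Removal is possible in both arms, with longer exposure in the immediate arm.

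A separate point concerns meaning. At week 2, a standard-arm woman following the plan has no implant, and at week 4 she may have none. Her answer about contraception then describes a bridging method or nothing, while an immediate-arm answer describes the implant.

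**Working it through.** The documents give no scale, expected rate, sample size or power for either satisfaction outcome, so there is no planned figure to reproduce. The check sets the sections against each other and then bounds the effect.

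**Who is still asked after the insertion window**

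| Woman | Rule | Later satisfaction rating |
|---|---|---|
| Implant placed and kept | none | Collected at 8, 12 and 24 weeks |
| Standard arm, waiting at week 2 or 4 | none; still enrolled | Collected, but does not describe the implant |
| Implant never placed | 15.1, natural reading: withdrawn | Not collected |
| Implant removed, either arm | 15.2: data collection ends | Not collected |

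**Whether another provision recovers the missing ratings**

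- Data kept from before withdrawal: for a never-inserted woman they do not describe the implant; for a woman with a removal they may come before the dissatisfaction that led to it.
- Intention-to-treat analysis: it cannot use ratings that were never collected.
- Retrospective survey: it covers missed contacts, but nothing extends it to withdrawn women.
- Chart review: it recovers breastfeeding and implant use, not satisfaction.
- Section 13.1: it has no rule for missing satisfaction scores.

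**Illustrative bound for the standard arm**

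From the plan: 75 women per group (Section 5.3). Assumed: share unscored q, and proportion satisfied among scored women s = 0.80. Let u be the unknown proportion satisfied among unscored women.

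All-randomised proportion = (1 − q) × s + q × u, with u anywhere from 0 to 1.

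| q | Women scored, 75 × (1 − q) | Lowest (u = 0) | Highest (u = 1) |
|---|---|---|---|
| 5% | 71.25 | 76% | 81% |
| 10% | 67.5 | 72% | 82% |
| 20% | 60 | 64% | 84% |
| 30% | 52.5 | 56% | 86% |
| 40% | 45 | 48% | 88% |

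Error of the scored-only figure = q × (s − u). At q = 20%:

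- u = 0.2: 0.20 × 0.6 = 12 points too high
- u = 0.6: 0.20 × 0.2 = 4 points too high
- u = 0.8: zero
- u = 1: 0.20 × (−0.2) = 4 points too low

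**Effect on the difference between arms**

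Assume 5% unscored in the immediate arm, 20% in the standard arm, and the same s = 0.80 and u in both. The scored-only difference is 0. The all-randomised difference, immediate minus standard, is (0.20 − 0.05) × (0.80 − u):

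- u = 0.2: 0.15 × 0.6 = 9 points
- u = 0.6: 0.15 × 0.2 = 3 points
- u = 0.8: 0
- u = 1: 0.15 × (−0.2) = −3 points

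The sign depends on u, which the documents do not give.

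**The case against.** A reader might infer that satisfaction can be scored only in women who hold an implant, and that standard-arm women awaiting insertion drop out. The documents do not support either. The listed item concerns contraception generally and is put to participants without restriction. Women awaiting insertion stay enrolled and are surveyed. A woman without an implant could also rate the timing she was assigned. The questionnaire wording is not in the documents.

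Nor does the plan say that implant or timing satisfaction will be compared at week 2, since Section 1.3.8 names no time point. That the standard arm has no implant then is a feature of the design. What stands is that the weeks 2 and 4 item should not be read as a rating of the implant in women not yet inserted.

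The bleeding figure in Section 2.3, item 1, where "approximately one in five women requested discontinuation of use due to irregular bleeding", is weak support for unequal loss. It counts requests in a retrospective cohort, carries no time frame, and is reported there as not significantly different between immediate and standard insertion. It suggests only that removal may not be negligible.

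The plan also limits the loss. Reminders and rescheduling reduce missed insertions, earlier data are kept, and an intention-to-treat analysis is planned. The wording of Section 15.1 is loose, so withdrawal for non-placement is its natural reading rather than an explicit rule. These are secondary outcomes, and the study is powered only for breastfeeding continuation. All of this lowers the priority, but none of it restores ratings from women who have been withdrawn.

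Finally, the aim in Section 2.3, item 7, is worded around women who had an implant inserted. That is a fair reason to keep a recipients-only result, and a reason not to replace satisfaction with a composite of uptake and satisfaction.

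**Conclusion.** The concern holds as follows. If Sections 15.1 and 15.2 are followed as written, comparisons of implant and timing satisfaction after the insertion window lose women on the basis of events after randomisation, and no other provision recovers their ratings. Removal is explicit and applies to both arms. Non-placement rests on the natural reading of Section 15.1 and should fall mainly on the standard arm.

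Size and direction cannot be fixed from the documents. With an assumed 20% unscored and 80% satisfied among scored women, the standard arm's all-randomised figure could be 64% to 84%. The bias is zero if unscored women are as satisfied as the others. It is tempting to conclude that the comparison must flatter standard timing. That needs unscored women to be less satisfied, which is plausible but not shown.

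Separately, the weeks 2 and 4 item does not measure the implant in standard-arm women not yet inserted. The point concerns unpowered secondary outcomes and merits a cheap improvement. It is no threat to the primary result.

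**What to change.** 1. **Sections 15.1 and 15.2:** state that non-placement or removal does not end questionnaire follow-up for women who still consent. Without this, the next two changes conflict with the withdrawal rules.
2. **Sections 1.3.8, 7 and 12:** name the timing-satisfaction item and put it to every randomised woman at 8 weeks, whether or not an implant was placed. Add it to the schedule and instruments table.
3. **Section 12:** record the satisfaction items at the contact where removal or non-placement is reported.
4. **Section 13.1:** compare timing satisfaction among all randomised women with a response, with the recipients-only result beside it. Report the number without a response by arm and reason.
5. **Weeks 2 and 4:** report the existing item by arm, descriptively, as satisfaction with current contraception.
6. **Composite:** any measure combining placement, continued use and satisfaction should be supportive at most, because it mixes uptake with satisfaction.

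The cost is a protocol amendment, possibly one added survey item, and a few more questionnaires from women without an implant.
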